6.4. Risks Identified in Behavioral Testing

Completing these measures may be anxiety-producing; these risks will be addressed by providing an appealing and quiet private area to complete the measures. All data will be kept confidential. The surveys do include questions regarding suicidality. If at any time during the assessment there is concern that a participant has suicidal ideation, the study team will immediately evaluate the participant. If the participant is felt to be a danger to themselves or others (via specific questionnaire responses or spontaneous reports from participant or parent), a study team member will escort them to the emergency department for further evaluation and management. Indications of child abuse will be followed up through notification of the hospital child abuse team and/or state authorities, as appropriate at each site.

6.5. Phlebotomy risks

Phlebotomy may result in transient pain, bruising or dizziness, as well as anxiety. There is a theoretical risk of phlebitis or infection which is uncommon. Phlebotomy will be performed by skilled pediatric research nurses, and a topical anesthetic will be offered to the participants. Families refusing phlebotomy despite encouragement will be allowed to participate in the rest of the study.

6.5.1. Burden to participant

PSG visits and daytime study visits will be scheduled during a time when children are stable and free of acute illnesses. Testing of neurocognitive/behavioral functioning is performed with regularly scheduled breaks during test administration to avoid excessive fatigue.

6.6. Potential Benefits to Participants and Others

There is prospect for direct benefit to participants, although it is possible that some or all participants will not receive direct benefits. Based on the nonrandomized smaller studies in children with MSDB, and the CHAT study on children with OSA beginning with an apnea hypopnea index as low as 2/hr, participants randomized to eAT may show

improvements in behavior, sleepiness and quality of life. It is also possible, based on adult data, that in children with MSDB, treatment will lower their cardiovascular risk profile²¹. Please see the rationale and Significance sections for a detailed description of the rationale for AT in improving behavior, sleepiness and quality of life in children with MSDB.

Participants randomized to WWSC may benefit by avoiding surgery if snoring and symptoms resolve without surgery or if the study shows that surgery does not improve behavioral outcomes.

In addition, all participants will receive information about healthy sleep habits for children. Children identified with obstructive sleep apnea during PSG may benefit from being screened for this study, but will ultimately be excluded from participation. Data collected for research purposes only (research PSGs, behavioral performance testing, behavioral rating scales and IgE level) will be made available to families, and the child's physicians after the study ends and may provide beneficial baseline information for future health concerns. Any data indicating a health risk will be made available to the child's physician as soon as those data are reviewed. The information obtained from this study will improve our understanding of the effects of MSDB on children's health, and will lead to better management, which is important as currently the management of MSDB varies widely across the country.

6.7. Alternatives

A discussion of alternative treatments (non-participation, other treatments available, and AT at the discretion of the ENT surgeon) will be presented at the time of informed consent.

7. Study Interventions

All participants, regardless of treatment assignment (eAT or WWSC) will receive the following interventions throughout the course of the trial:

7.1. Sleep and Healthy Lifestyle Education

Educational material on healthy sleep habits will be provided to each participant at the baseline visit after research data are collected. Standardized materials recommended by the National Institute of Health and pediatric professional sleep societies will be used to reinforce optimal sleep healthy and educational play will also be encouraged by providing take-home materials.

7.2. Other Supportive Care

At initial evaluation (and as needed throughout the course of the trial), participants identified by the site principal investigator as having suboptimal asthma or allergy control will be referred to their primary care physician for management and further treatment of these problems.

8. Procedures Specific to Treatment Arm Assignment

8.1. Surgical Treatment – Early Adenotonsillectomy (eAT)

Within 1 to 4 weeks of randomization, participants randomized to the eAT arm will undergo AT under general anesthesia, as occurs as part of usual care. Surgery will be performed by board-certified otolaryngologists with or without the assistance of resident physicians in accredited otolaryngology training programs.

Prior to the surgical procedure, tonsillar size will be graded using a standardized scale of 0-4 as described above. Extent of adenoid tissue will also be graded as mild (0-33%), moderate (34-66%) or severely (67-100%) obstructing the posterior choanae. Complete bilateral tonsillectomy and removal of obstructing adenoid tissue will be performed by cold dissection, monopolar electrocautery or any other recognized surgical technique. Further details of surgical intervention and quality monitoring of surgical intervention will be outlined in the Surgical Quality Control Manual of Procedures.

8.2. Participants Randomized to Watchful Waiting with Supportive Care

After 12 months, children who did not get surgery who have a 12-month PSG showing obstructive sleep apnea (apnea hypopnea index >or =3.0 /hr or obstructive index > 1/hr) or whose parent reports ongoing symptoms/concerns will be referred back to ENT for further clinical management (such as adenotonsillectomy) as per standard clinical care.

9. Study Procedures

A study visit schedule is provided in Appendix A. Visit time points, study procedures and assessments are listed in the order in which they occur.

9.1. Polysomnography (PSG)

All children will undergo standardized screening PSG at study entry to determine eligibility, and at the 12 month visit.

9.1.1. PSG Methods Overview

Each clinical site will use a standardized approach as established in training. Existing laboratory equipment will be used, but data will be standardized by using the same montage and similar sensors, sampling rates and filters. Sleep technicians who collect PSG data for this study will be supervised by a lead technician who was certified by central training for technical proficiency to collect research PSG data for this trial, or someone trained by a centrally certified technician. Participants will report to the sleep laboratory 1 hour before their usual bedtime and remain at the sleep laboratory in a quiet dark room until the study ends the following morning at their spontaneous wake time. Children must be accompanied by at least one parent/guardian during the night. Weekend slots will be made available, as feasible, to families to facilitate recruitment. The completed PSG will be exported as a standardized European Data Format (EDF) file and electronically transmitted to an FTP server at the central Reading Center for standardized scoring.

9.1.2. Screening PSG

All potential participants who meet the initial eligibility criteria will be evaluated through a standardized PSG prior to the baseline exam. PSG results that do not meet AHI/saturation criteria after central review by the Reading Center are ineligible for participation regardless of the local clinical interpretation of the PSG data and the baseline visit will not be scheduled. Baseline PSG data can be obtained in two ways:

1. A proportion of PSGs may have been performed as part of routine clinical care. PSG data (performed for clinical purposes within 60 days prior to the baseline/randomization visit) will be transmitted to the Reading Center where they will be re-scored to ascertain PSG eligibility and entry into the study. If a clinical PSG has been performed more than 60 days prior to baseline/randomization or was not performed using agreed upon research sensors and montages, then a research PSG must be performed.
2. Potential participants who have not undergone a PSG within 60 days prior to the baseline/randomization visit will undergo a research PSG. Resulting PSG data will be transferred to the Reading Center within 48 hours to determine PSG eligibility and to collect research quality data.

9.1.3. 12 Month Endpoint PSG

2 weeks before or 2 weeks after the scheduled Month 12 daytime visit, all participants will undergo a research PSG. Data will be transmitted to the Reading Center and results will be scored (refer to the PSG Manual of Procedures).

9.1.4. Scheduling the PSG

One to two days prior to each scheduled PSG, families will be contacted to remind them of the visit and to ensure that intervening medical illnesses have not occurred, requiring the visit to be rescheduled. These include any of the following within the previous 7 days:

- febrile illness
- upper respiratory illness resulting in increased coughing
- acute nasal problems
- asthma exacerbation

9.1.5. PSG Procedures

Children will be encouraged to maintain their usual daily routine prior to PSG. Lights off will be at approximately 2000-2100 (depending on age) and lights on no earlier than 0600. Neither sedation nor sleep deprivation is used to induce sleep.

9.1.6. Montage

The following are monitored: Sleep architecture (6 EEG sites [F₃/M₂, F₄/M₁, C₃/M₂, C₄/M₁, O₁/M₂, O₂/M₁], bilateral electro-oculograms [EOG: ROC/A₂, LOC/A₁], submental electromyography [EMG]; airflow by oronasal thermocouple (Pro-tech);

nasal pressure cannula (Pro-tech); snoring sound (microphone by Pro-tech, a vibration flow sensor, or a battery operated Tascam microphone; respiratory effort (chest and abdominal wall inductive plethysmography); end-tidal CO₂ (capnography waveform and numeric display); pulse oximetry (numeric and plethysmograph waveform in the 2 sec averaging mode); ECG with a standard 3-lead precordial placement; leg movements (bilateral tibial EMG); body position.

- When possible, EEG, EMG, and EOG signals will be sampled at rates designated as “desirable” by The AASM Manual for the Scoring of Sleep and Associated Events Version 2.2 (EEG, EOG, EMG, ECG and snoring at 500 Hz, respiratory signals at 100 Hz, and oximetry at 25 Hz).
- When equipment precludes collecting data at “desirable” rates, all data must at least meet the AASM 2015 “minimal” sampling rate criteria (EEG, EOG, EMG, ECG and snoring at 200 Hz, respiratory signals at 25 Hz, and oximetry at 10 Hz).

9.1.7. Central Transmission of PSG Data

The PSG will be exported in EDF format and transmitted to a sFTP server at the Reading Center for standardized scoring within 2 business days. If PSG urgent referral criteria are identified (i.e., on baseline/screening PSG, severe levels of obstructive sleep apnea precluding randomization; or on follow-up PSG, levels that exceed adverse event thresholds), the data will be reviewed by the Reading Center Director. An Urgent Referral Alert form will be completed and transmitted to the clinical site for follow-up. The clinical site will provide this information to appropriate physicians and family members for clinical follow up (refer to PSG Manual of Procedures).

9.2. Study procedures and details of the baseline visit

Following confirmation of initial eligibility including screening PSG, participants will be scheduled for a baseline morning visit with consideration for any intervening medical illnesses (30 days from the time of an acute exacerbation of illness requiring hospitalization or systemic steroids or 14 days from the time of a fever or an illness of sufficient severity that it required the child to miss 2 or more days of school/pre-school or be confined to bed for 2 or more days).

Visits should aim to begin between 8:00-9:00 AM and no later than 11 AM. The evaluation will generally last no more than 4.5 hours. Participants will be encouraged to follow their usual bedtime routine the night prior to testing. Participants will undergo the following, in the order listed:

- Brief orientation to testing facility
- Urine collection for cotinine
- Resting morning blood pressures in triplicate
- Anthropometry
- Brief physical examination by the study physician or designee
- Breakfast/snack and rest period
- Behavioral performance testing by child and questionnaire completion by parent
- Brief rest period

- Venipuncture (note: fasting not required)
- Randomization

The Research Coordinator will also review and provide an appointment schedule and reaffirm the importance of maintaining the blind.

9.2.1. Orientation

On arrival to the research facility, participant and parent/legal guardian (s) will be introduced to the research staff and provided with a brief tour of the facilities, using child-friendly approaches.

9.2.2. Urine collection for cotinine

The child (with the assistance of the parent) is instructed to void into a collection device (urinal, “hat”, or bedpan). Study staff transfers the specimen to a non-sterile container. Following instructions outlined in the Laboratory MOP, the specimen is stored locally at -80°C and shipped on dry ice to the central laboratory at Children’s Hospital of Philadelphia Clinical and Translational Research Center as per the schedule in the Manual of Procedures.

9.2.3. Morning blood pressure

After a 5 minute rest period, while the child is sitting, systolic and diastolic BP will be measured 3 times, at least 60 seconds apart, according to standardized guidelines. Cuff size will be determined by measuring the circumference of the upper arm, measured at the midpoint, and identifying the appropriate bladder size from a standard chart

9.2.4. Anthropometry

Parent/caregiver will be instructed to have the child wear loose clothing to the visit. Weight (to 0.1 kg) will be measured on a calibrated digital electronic scale. Standing height (to 0.1 cm) will be measured with a stadiometer, and neck, waist and hip circumferences will be obtained to determine regional fat distribution, as outlined in the Anthropometry MOP. Measurements will be repeated three times, and average values will be utilized, as defined in the MOP.

9.2.5. Physical examination

The Principal Investigator/designee will review the participant’s medical and sleep history and perform a brief standardized physical exam, including standardized assessment of tonsillar size, evaluation of the oropharynx using Friedman and Mallampati position scales, and identifying any abnormalities on heart, lung, neurological and ears, nose and throat assessments.

9.2.6. Breakfast/Snack and rest period

The child will be provided with a snack and a brief break.

9.2.7. Behavioral performance testing and questionnaire completion

Behavioral performance testing will take approximately 20 minutes for the child and questionnaire completion will take approximately 90 minutes for the caregiver. Testing will be administered by a Research Coordinator who is centrally trained, certified by the Neurobehavioral Quality Control Committee, and blinded to the treatment arm. Tests will be performed in the same order. Testing will be performed in a private, quiet room with adequate lighting and table space. Breaks are built into the testing sequence to avoid excess fatigue. The parent will complete the questionnaires in a separate room while their child is being tested, on a computerized system. The child will be supervised in a hospital play room, with a Child Life therapist, or other appropriate site and personnel, while the parent completes the surveys. All tests will be performed as outlined in the Behavioral Testing MOP. The Research Coordinator will be available for assistance, and will ensure completion of all tests at the end of the session.

We will provide families with paper forms that can be mailed or emailed back to the study coordinator. Blinded coordinators will instruct the parent not to provide any personal identifiers on paper forms and the RC will check the forms for PHI and remove any if found. Families will also be given the opportunity to complete these questionnaires electronically. An email link to the SLICE data management system will be sent to parents for remote completion of neuro-behavioral forms, SLICE is managed by the DCC. The SLICE Data Management system has a safeguard that will not allow parents to enter PHI directly into the system. CBCL for children 6 years and older, the only measure that assess for suicidal ideation, will be completed during an in person visit only with a blinded RC. These alternatives meet CHOP IT standards and are critical to have a complete dataset in all participants.

Child Performance Testing

- NIH Toolbox 9-Hole Pegboard Dexterity Test (a test of fine motor coordination)
- Go-No-Go Continuous Performance Task (GNG), a test of sustained attention (vigilance).
- PedsQL: Children \geq 5 years of age also complete the child version of the PedsQL, a generic measure of global quality of life

Parent Questionnaires (note that several measures utilize a date stamp when questionnaires are entered electronically into the commercial scoring websites)

- Behavior Rating Inventory of Executive Function (BRIEF2/P), a measure of executive function (the global score a co-primary outcome). The BRIEF-P is for use in pre-school children.
- Child Behavior Checklist (CBCL), a measure of behavior
- Conners Third Edition Short Form, a measure of attention-deficit/hyperactivity disorder symptoms (parents of children \geq 6 years of age only)
- Adaptive Behavior Measure System, 3rd Edition (ABAS-III), a measure of children's everyday functioning (this measure is centrally scored, and date of birth as well as date of study and study ID is required to be entered into the WPSpublish website)

- Epworth Sleepiness Scale modified for children, a measure of daytime sleepiness
- Pediatric Quality of Life Inventory (PedsQL; parent form), a generic measure of global quality of life
- OSAS-18, a measure of disease-specific quality of life
- Pediatric Sleep Questionnaire Sleep-Related Breathing Disorder Scale (PSQ-SRBD scale), a measure of symptoms of SDB, including nighttime and daytime symptoms.
- Family Assessment Device, a measure of family functioning
- Parenting Style Questionnaire, a survey of the type of parenting style
- Parenting Stress Index 4th Ed., Short Form, a measure of parents' perception of stress
- Rapid Estimate of Adult Literacy in Medicine, Revised, a measure of patient (caregiver) health literacy (only at baseline visit)
- Experiences of Discrimination, a measure of experiences with racism
- International Study Of Asthma And Allergies In Childhood (ISAAC), a survey to determine the presence of asthma, rhinitis and eczema
- Asthma Severity Survey, a measure of asthma exacerbations and controller therapy based on items from the Composite Asthma Severity Index (only for children with ISAAC Global Wheezing Score ≥ 5)
- COVID-19 Survey

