2.2. Study Schema

6-month visit, remote collection of parent behavior assessments at all sites except Virginia

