2.4.3. Follow-up Contacts

eAT arm only: AT surgery 1-4 weeks from randomization within Month 1

WWS arm only: ENT re-evaluation visit with 1-4 weeks after Endpoint Visit if indicated by 12-month PSG revealing obstructive sleep apnea (AHI ≥ 3.0 /hr. or obstructive apnea index > 1 /hr.) or parent reporting concerning symptoms.

Both groups:

- Monthly contact by telephone, email and/or text messaging , for health care utilization, medication, adverse event inquiries and to support study participation.
- Check In questionnaires and surveys will be completed bi-monthly, at months 2, 4, 6, 8, and 10.
- Interim remote visit at 6 months for caregiver questionnaires and neuro behavioral assessments, adverse event and health care utilization inquiry, and teacher forms of behavior rating scales.
 - Virginia will have in person child neurobehavior testing in addition to assessments above.
- Endpoint Visit at Month 12 for behavioral and performance testing; questionnaires; anthropometry, and BP measures. Behavioral rating scales mailed to teachers.
- Follow-up research PSG at Month 12
- Follow up questionnaires after participation ended to assess feasibility of conducting a study to evaluate long-term outcomes of mild SDB

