9.9.2. Urgent Medical Referral Criteria

Conditions that will generate an Urgent Medical Referral Alert are those laboratory, physiological or behavioral findings that are believed to represent conditions that may require additional evaluation by the participant's health care providers in a timely manner. Because the participants in this study are pre-screened to be "otherwise healthy" children, most participants who meet Urgent Medical Referral Criteria are likely to be encountered at the time of their screening PSG and will no longer be eligible to participate and will exit the study to routine or urgent health care, as appropriate.

NOTE: At the baseline visit, one of the behavioral questions asks about suicidal ideation. A positive endorsement of that symptom will lead the study team to prompt assessment, deferred participation and possibly exclusion from the study, as appropriate for the participant's welfare. CBCL for children 6 years and older, the only measure that assesses for suicidal ideation, will be completed during an in person visit by the blinded RC only.

If the following conditions are identified during the course of the study, their occurrence will generate an Urgent Medical Referral by the Site PI who will communicate with the participant's parent or guardian, and with permission, contact the child's health care provider. Some of these conditions (abnormalities of blood pressure) will be noted as usually needing confirmation with repeat testing before clinical decision making.

- Stage 2 hypertension (> 99% for age and gender)
- PSG: Desaturation to < 90% for > 2% of total sleep time OAI >20/hr. or AHI > 30/hr.
- ABAS-3 score of <60
- Suicidal ideation

It should be noted that if any of these conditions occur after enrollment (i.e., not during a screening visit that disqualifies the child from enrolling in the study), these conditions will also be reported as Adverse Events.

An *Urgent Medical Referral Alert* should be completed and the site PI notified within 24 hours of first knowledge of the event.

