10.4.5. Behavioral testing

If at any time during the assessment there is concern that a participant is reported by his/her parent/caregiver to have suicidal ideation, the study team will immediately evaluate the participant. The Neurobehavioral Subcommittee has developed a plan for suicidal ideation and suspected child abuse. Each site has modified this to specify local individuals and mechanisms for referral. All site-specific plans identify the primary professionals who will be contacted in the event of suicidal ideation or suspected child abuse, as well as backups when the primary is unavailable. These professionals will be responsible for contacting and working with local mental health staff. All sites also identify the local department that participants will be escorted to by PATS staff if the primary and backup professionals cannot be contacted. The CBCL for children 6 years old and older, the only measure that assesses suicidal ideation, will be completed in the presence of a blinded RC only.

Participant Refusals, Screen Failure, Withdraws, Discontinuation, and Missed Appointments

11. Participant Refusal

A record will be kept of all participants and parent/legal guardian (s) who are approached but refuse to participate in the study prior to signing the Informed Consent. For tracking purposes, the reason for refusal will be documented on the Screening Log.

12. Withdraw/Premature Termination

If a participant withdraws/terminates from the study prior to the 12-month visit, every effort should be made to obtain follow-up safety data which includes information on adverse events and current health status including sleep habits and surgical AEs (if applicable). The clinical site must also complete the Study Stop CRF [SSTOP] indicating the reason for termination.

13. Missed Appointments

If a participant does not keep a scheduled appointment, the missed visit (testing) must be rescheduled within two weeks.

To minimize the occurrence of missed appointments the parent/legal guardian will be provided with the following reminders when appropriate:

- Written schedule of visits during the baseline exam
- Printed card with date of next visit or contact (when appropriate)
- Phone notification within 1 to 2 days prior to the scheduled visit
- Letter via postal mail if other methods of communication fail

14. Quality Assurance

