Following 12 months, participants in the WWS group will be referred to ENT for a clinical visit, if their 12-month PSG shows an AHI \geq 3 /hr or obstructive apnea index > 1/hr. or if the parent/caregiver reports concerns or symptoms. The 12-month end point was chosen to enable assessment of long-term therapeutic effects. However, data from the 6-month visit will be used to improve the study's statistical efficiency; help identify the time-course and trajectory of treatment response; and provide information for imputing missing 12-month data. In addition to the efficacy analyses described below, adverse events will be summarized and presented by treatment groups.

Aims, Hypotheses and Endpoints

Aim 1: To determine the effect of eAT on behavior, attention, SDB symptoms, sleep quality, and quality of life in children with MSDB.

Aim 2: To determine the effects of eAT on health care utilization (HCU) in children with MSDB.

Aim 3: To identify factors that moderate the response to AT, including age, asthma/atopy, obesity, secondhand smoke exposure, sleep duration, family functioning socioeconomic status, and race.

Endpoint for Primary Efficacy Hypotheses

The co-primary outcome of the randomized controlled trial will be the GEC Score from the BRIEF2/P and the GNG. Please see the CCC application for details on its reliability, responsiveness, and psychometric properties.

Primary Null Hypothesis

The primary null hypothesis is that the mean change at 12 months in the BRIEF2/P GEC Score and GNG sustained attention d' will be the same for children who were randomized to eAT or to WWS.

Secondary Null Hypotheses

- a) There will be no difference between treatment groups in the expected mean change at 12 months in other behavior/performance measures, SDB symptoms, and quality of life.
- b) There will be no difference between groups in expected HCU (illness or injury requiring hospitalizations; emergency department visits; inpatient procedures; outpatient procedures; scheduled office visits; unscheduled office visits or urgent care visits; medication use) during the 12-month study period.

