Our approach will involve close collaboration between clinical experts and biostatisticians while ensuring appropriate blinding. Interim analyses of baseline variables (aggregated across intervention groups) will be conducted early in the study to ensure that the collected and derived data follow the assumed distributions, and that appropriate methods for identifying outliers and for computing clinical scores are implemented. Reports will provide a full description of the distributions of each study variable, along with indices of associated data quality, and include graphic displays. The amount and patterns of missing data, if any, will be characterized. Measures that are not normally distributed may be transformed to meet model assumptions. In some instances, such as symptom summaries for related outcomes, outcomes may be derived by combining several variables into a small set. Before conducting final analyses, descriptive statistics will be generated using the total data set, ensuring that outliers or potential discrepancies in the data are resolved.

Descriptive Comparisons between Treatment Groups, Baseline and Over Time

Descriptive analyses will be performed to characterize the treatment groups, and to confirm that the randomization resulted in no important group differences at baseline. Summary statistics such as means, medians, standard deviations, and ranges also will be used to describe changes from baseline to Month 6, and from baseline to Month 12, for all primary and secondary outcome variables within each treatment group, as well as to describe dropout rates, treatment failures/cross-over rates, and patterns of missing data. Graphical methods such as stem-and-leaf diagrams, box plots, and scatter plots, will be used to examine distributions, and guide the choice of transformations. Two-group comparisons will generally employ Wilcoxon rank-sum tests to protect against violations of normality assumptions. Categorical variables, including dichotomous factors, will be summarized by proportions, and compared among groups using Fisher's exact test.

Statistical Approaches to Testing for Treatment Differences

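### The SAP assumes month-6 data for every non-PSG outcome, but the parent CBCL for children aged 6 and over cannot be collected at a remote month-6 visit, so its month-6 estimate is age-selected

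*Combined protocol and SAP*

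**What the plan says.** **How the parent CBCL is collected.** Section 9.2.7: "CBCL for children 6 years and older, the only measure that assess for suicidal ideation, will be completed during an in person visit only". Section 9.9.2 agrees: it "will be completed during an in person visit by the blinded RC only". Section 10.4.5 is looser: it "will be completed in the presence of a blinded RC only".

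**How month 6 is conducted.** The schema in section 2.2 reads "6-month visit, remote collection of parent behavior assessments at all sites except Virginia". Section 2.4.3 lists an "Interim remote visit at 6 months for caregiver questionnaires and neuro behavioral assessments", with in-person child testing added in Virginia. Section 2.1 says the same, the heading of 9.7.4 calls the visit remote, and the compensation plan in 5.3 pays for a remote month 6. Two places point the other way. The COVID-19 note inside 9.7.4 treats a virtual visit as the fallback, and Appendix A labels month 6 a clinic visit with blood pressure and anthropometry marked.

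**How the data are to be used.** Section 3.2 lists the CBCL, parent and teacher forms, as a secondary endpoint. The SAP will "describe changes from baseline to Month 6, and from baseline to Month 12, for all primary and secondary outcome variables" and will use month 6 to "help identify the time-course and trajectory of treatment response". Under Secondary Analyses, Aim 1, it says that everything except the PSG indices will be on hand at both follow-up visits. On that basis it plans the model with visit as a category and, where the course looks linear, a slope model over 0, 6 and 12 months. Comparisons are adjusted for the stratification factors, which include age cut at 5 years. No age-by-visit or age-by-visit-by-treatment term is stated.

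**The concern.** Read together, these rules leave the parent CBCL complete at baseline and month 12 for all ages. At month 6 it exists only for children still under 6, plus Virginia. A child outside Virginia who turns 6 before month 6 also loses that assessment. The gap is set by age, and age is a moderator the trial plans to test (Aim 3). The rationale section argues that preschool children may be the most likely to improve if treated early.

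The month-6 effect would therefore describe mostly younger children and the month-12 effect all children. If benefit differs by age, that difference can appear as benefit fading or growing between visits when nothing has changed. The SAP neither recognises the gap nor includes a term that could absorb it. Its general missing-data text does not identify this as data absent by design.

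**Working it through.** **1. The plan's own counts.** 460 × (1 − 0.15) = 391 (stated: 390). 460 × (1 − 0.20) = 368 (stated: 368). Both reproduce to rounding. The documents give no CBCL-specific count.

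**2. Month-6 parent CBCL coverage.** Let p be the share under 6 at month 6 and v Virginia's share of children, with the same age mix at all sites. Coverage is c = p + (1 − p)v, and the share under 6 among those observed is p/c.

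- The SAP expects 50% under 5 years and does not give the share aged 5. Assumed p = 0.50 to 0.60.
- The study summary gives 7 sites and the SAP 5, with no site sizes. Assumed v = 1/7 to 1/5.

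| p | v | c | Children, of 390 | Absent | p/c |
|---|---|---|---|---|---|
| 0.50 | 1/7 | 0.571 | 223 | 167 | 0.875 |
| 0.50 | 1/5 | 0.600 | 234 | 156 | 0.833 |
| 0.60 | 1/7 | 0.657 | 256 | 134 | 0.913 |
| 0.60 | 1/5 | 0.680 | 265 | 125 | 0.882 |

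**3. Expected estimates from the planned model.** Assume effects E_u (under 6) and E_o (6 and over), in points of improvement and constant over time, with within-child correlation ρ = 0.6 under compound symmetry. None of these values is in the documents. Write s = 1 − p.

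- Effect among children observed at month 6: E_obs = (p·E_u + s·v·E_o)/c.
- All-age effect, which is also the month-12 estimate: E_all = p·E_u + s·E_o.
- The model in effect predicts an absent month-6 score from the child's baseline and month-12 scores, each with weight k = ρ/(1 + ρ) = 0.6/1.6 = 0.375. Baseline means are equal by design, so the month-6 estimate is E_obs + k(E_all − E_obs).

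The ends of the range for s = 0.30 to 0.50 are:

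| E_u / E_o | s, v | E_obs | Month 12 (E_all) | Model month 6 | Apparent change |
|---|---|---|---|---|---|
| 4 / 1 | 0.30, 1/5 | 3.763 | 3.10 | 3.51 | −12% |
| 4 / 1 | 0.50, 1/7 | 3.625 | 2.50 | 3.20 | −22% |
| 1 / 4 | 0.30, 1/5 | 1.237 | 1.90 | 1.49 | +28% |
| 1 / 4 | 0.50, 1/7 | 1.375 | 2.50 | 1.80 | +39% |
| 3 / 2 | 0.30, 1/5 | 2.921 | 2.70 | 2.84 | −5% |
| 3 / 2 | 0.50, 1/7 | 2.875 | 2.50 | 2.73 | −9% |

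A full generalised least squares calculation of the model gives the same figures. If E_u = E_o, then E_obs = E_all and neither visit estimate moves.

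The range of s is wider than in step 2. At s = 0.30, coverage would be 0.70 + 0.30/7 = 74% to 0.70 + 0.30/5 = 76%.

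The 4 v 1 pair is illustrative but compatible with the one CBCL figure in the documents. With 47% aged 6 or over it averages 0.53 × 4 + 0.47 × 1 = 2.59. The earlier trial in children with OSA found 3.8 − 1.2 = 2.6.

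**4. What moves.** The average of the two visit effects moves by half the month-6 shift. For 4 v 1 with s = 0.50 and v = 1/7 it is (3.20 + 2.50)/2 = 2.85 against a true 2.50. The month-12 contrast did not move in any scenario. The slope-by-treatment coefficient moved by less than 0.1 point per 6-month step.

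**The case against.** The case on the other side has five parts.

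- **The visit mode is not settled.** Appendix A and the COVID-19 note suggest an in-person month 6, and section 10.4.5 asks only for a blinded coordinator's presence. This stands as a reason to reconcile the text. It does not remove the point, because any month-6 visit held remotely loses the parent CBCL in older children under sections 9.2.7 and 9.9.2.
- **A reader might infer that month-6 CBCL is essentially an under-6 measure.** That goes too far. Virginia contributes older children, so the under-6 share is about 83-91%. The teacher form is mailed at baseline, month 6 and month 12 with no age or in-person limit (section 9.4 and the Appendix A notes).
- **A reader might take the raw contrast as the bias.** For 4 v 1 that is 4.0 at month 6 against 3.1 to 2.5 at month 12, or 23-38% waning. This ignores Virginia and the model's use of month-12 scores. The planned model gives 12-22%.
- **A reader might conclude that the slope model should be dropped.** The calculation does not support that, and the SAP makes the slope model conditional on an apparently linear course.
- **The stakes are limited.** The SAP calls secondary analyses exploratory, and it plans to describe missing-data patterns and run sensitivity analyses. This stands and lowers the importance. However, generic missing-data language does not correct a statement that the data will be there.

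**Conclusion.** The SAP's availability statement is wrong as written for the parent CBCL. That follows from the text alone, if month 6 is remote outside Virginia as most of the protocol says. The coverage figures (57-68% observed, 83-91% of them under 6) rest on assumed age and site shares.

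The bias is conditional. It affects the month-6 estimate and the two-visit average, and only if the effect differs by age. Under the assumed effects it amounts to 12-22% apparent waning, a 28-39% apparent rise, or 5-9% waning for the milder 3 v 2 pair. A lower within-child correlation would make it larger. The month-6 comparison is still randomized among the children observed. The documents do not support extending the point to the month-12 contrast, the teacher CBCL, the co-primary endpoints or the slope coefficient. Importance is low to moderate: this is one exploratory secondary outcome, and the correction is cheap.

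**What to change.** 1. Correct the statement under Secondary Analyses, Aim 1, so that it excepts the parent CBCL at month 6.
2. Reconcile the month-6 visit mode across section 2.4.3, section 9.7.4 and Appendix A, and the wording of 10.4.5 with 9.2.7 and 9.9.2.
3. For the parent CBCL only, declare month 6 missing by design for children aged 6 and over who are seen remotely. Make baseline-to-month-12 the only all-age contrast.
4. Report month 6 as an under-6 analysis, compared with month 12 in the same children. Define the set by age at the scheduled month-6 date, which is fixed at randomization. Alternatively, include age-by-visit-by-treatment terms. The month-6 estimate for older children would then rest on Virginia, about 22 to 39 children: 390 × 0.40 × 1/7 to 390 × 0.50 × 1/5.
5. Keep the all-age month-6 analysis of the teacher CBCL.

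The cost is some SAP wording and one restricted analysis set. The loss is an all-age month-6 parent CBCL estimate, which the planned collection could not properly support. The in-person safety rule is left as it is.
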